Antibiotic exposure is not reduced. Taking this finding in isolation, we would not recommend procalcitonin guideline implementation. However, if this finding is due to lower control arm antibiotic use relative to common clinical practice, we would conclude hospitals could choose either procalcitonin guideline implementation or compliance with current guidelines to reduce antibiotic use.

Antibiotic exposure is reduced, but safety worsens. Under this situation, we would not recommend widespread procalcitonin guideline implementation, but would analyze our composite adverse outcome results to determine if select adverse outcomes drive the overall finding, and if these outcomes occur predominantly in certain patient subgroups (e.g., elderly patients or those presenting with high PSI scores).

iii. MONITORING

a. DATA MONITORING

The ProACT Data Safety and Monitoring Board (DSMB), chosen by the funding source, the National Institute of General Medical Sciences (NIGMS), will provide a multidisciplinary, independent review of the study design, ethical and scientific conduct of the study, monitor interim results and make recommendations with respect to continuation, modification, and termination of the study. Each individual is an experienced academician and together will provide clinical, research, and statistical expertise. The DSMB will meet at two planned interim analyses for safety, at completion, and at any other needed interval.

b. HARMS

Event reporting

We will capture the major potential adverse events related to antibiotic withholding in our combined primary safety outcome. With this in mind, **the adverse outcomes that comprise the primary safety outcome will be included in outcome reporting, and will not be reported a second time as AEs or SAEs.**

However, as with any experimental procedure, there may be adverse events that are currently unknown and certain of these unknown risks could be permanent, severe, or life threatening.

Monitoring of adverse events (AEs) is critical to the participant's safety and data integrity. An adverse event will be defined as any untoward medical occurrence (unfavorable and unintended sign, symptoms, or disease) in a participant temporarily associated with the study intervention or other aspects of study participation, but not necessarily considered related to the participant's participation in the research study. An untoward medical occurrence that: (1) results in death, (2) is life-threatening, (3) requires hospitalization or prolongation of existing hospitalization, or (4) results in disability/incapability will be defined as a serious adverse event (SAE).

All adverse events (AEs and SAEs) occurring after study enrollment until the study day 30 follow-up visit will be recorded.

AEs and SAEs will be recorded when reported by the participant, attending physician or site SC or PI, or when documented in the medical record. When a reportable SAE occurs, it will be the site PI's responsibility to review the pertinent records, notes, laboratory and radiographic data. This information will be recorded on the eDCF along with the site PI's impression of the diagnosis. The site PI will assess causality between the event and the study interventions using their best clinical judgment. **Notification of coordinating center regarding any AE that is serious, unexpected and related (possibly, probably or definitely related) to the study intervention will take place within 48 h of recognition (expedited reporting);** in addition, a copy of all documents submitted to the site IRB will be sent to the coordinating center.

A reportable AE or SAE that also meets **ALL** of the following criteria is also required to be reported as an Unanticipated Problem (UAP) Involving Risk to Human Subjects or Others as per local site IRB reporting procedures:

1. unexpected in terms of nature, severity, or frequency;
2. related, or possibly related, to a participant's participation in the research;
3. places participants or others at a greater risk of harm (including physical, psychological, economic, or social harm) that was previously known or recognized.

“Other” Unanticipated Problems (UAPs) Involving Risk to Subjects or Others

As per local study site IRB reporting procedures, this category includes all other incidents not previously included in the above AE reporting section and can include protocol deviations, non-compliance, or other unanticipated problems **that place subjects at risk of harm**.

This includes any accident, experience, or outcome that meets **ALL** of the following criteria:

1. Unexpected in terms of nature, severity, or frequency;
2. Related, or possibly related, to a participant's participation in research;
3. Places participants or others at a greater risk of harm (including physical, psychological, economic, or social harm) than was previously known or recognized.

Incidents falling into this category that require reporting to the ProACT Coordinating Center include:

- Enrollment of a participant that did NOT meet inclusion or met exclusion criteria
- Incomplete or lack of participant written consent
- Breach of confidentiality
- Incomplete data collection

Non-Compliance

Protocol deviations and incidents of non-compliance, which do **NOT** involve risk to participants or others must be reported as “Non-compliance” as per local site IRB reporting procedures.

Protocol deviations that require reporting to ProACT Coordinating Center by the local study site via eDCF documentation:

- Deviating from the protocol without risk to the participant
- Obtaining consent using an outdated consent form with no other substantive difference other than the date

Please Note:

- Incidents of non-compliance on the part of the research participant which do not involve risk do NOT need to be reported to the ProACT coordinating center.

Notification of DSMB

The ProACT coordinating center will be responsible for notifying the DSMB regarding all event reporting. The ProACT coordinating center will notify the DSMB and the University of Pittsburgh IRB within 48 hours of their knowledge of all AEs that are categorized as serious, unexpected and related.

All other reportable events will be recorded on the DCF, entered into the database and reported to the DSMB in routine reports. The DSMB will request any follow-up information they feel is necessary and will recommend modifications to the study protocol or consent as necessary.

c. INTERVENTION ADHERENCE

To improve intervention adherence, we will focus site start-up and education efforts on the key logistics steps required to accomplish the intervention. We will regularly monitor time to procalcitonin reporting (e.g., time to blood draw, lab receipt, assay time, assay completion to reporting) and receipt by clinicians (coordinators will document information receipt).

We will also conduct basic in-servicing to raise clinician awareness of the study and the procalcitonin algorithm. Our primary in-servicing message will be “Please look at the procalcitonin value and algorithm recommendation – the final antibiotic decision is entirely yours.”

d. AUDITING

We will conduct ProACT in compliance with all federal regulatory requirements, ensuring compliance. Site monitoring will consist of internal monitoring of the research database and external/on-site monitoring of source documents. Internal monitoring will consist of missingness checks for completeness and chronology, logic checks for accuracy, and trend analysis to identify problem areas. External monitoring will consist of site visits to evaluate human subject protections and source documents. Monitoring will be done by the ProACT project management team. The first site visit will occur after initial enrollment to verify consent procedures, participant eligibility, reported data, and IRB compliance. If a problem is identified during the visit (i.e. poor communication with the ProACT coordinating center, inadequate or insufficient staff to conduct the study, missing study documents) the monitor will assist the site in resolving the issues. Data verification for primary outcomes will be a priority during monitoring visits. A follow-up site visit will be conducted if a site is found to have continued and/or excessive issues. We will conduct regular site audits to determine reasons for study intervention non-adherence and procalcitonin algorithm non-adherence (e.g., patient condition worsening).

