[figure not shown]

TITLE: Procalcitonin Antibiotic Consensus Trial (**ProACT**)

NCT# NCT02130986

FINAL PROTOCOL DATE: Version 1.4, March 8, 2017

ProACT

(Procalcitonin Antibiotic Consensus Trial)

PI: [name], MPH
Director, Multidisciplinary Acute Care Research Organization (MACRO)
Associate Director, Abdominal Organ Transplant ICU
CRISMA Center
Department of Critical Care Medicine
Department of Emergency Medicine
Clinical and Translational Science Institute
[name]
[name]
University of Pittsburgh
[name], USA
[contact] (office)
[contact] (fax)

ProACT Trial Registration Data

Primary registry and trial identifying number:	ClinicalTrials.gov
Date of registration in primary registry:	May 1, 2014
Primary sponsor:	National Institutes of General Medical Sciences (NIGMS) (1R01GM101197 and 1R34GM102696)
Contact for public inquiries:	[name], BS [contact]
	[name], BS, BA [contact]
Contact for scientific inquiries:	[name] MPH [contact]
Public title:	Procalcitonin Antibiotic Consensus Trial (ProACT)
Countries of recruitment:	United States
Health condition(s) or problem(s) studied:	Procalcitonin-guided antibiotic use in lower respiratory tract infection (LRTI)
Intervention(s):	Experimental: Reporting of serial procalcitonin results and antibiotic guideline to treating clinicians. Clinicians retain complete decision-making autonomy. Control: Usual care; no procalcitonin results will be reported to treating clinicians.
Key inclusion and exclusion criteria:	Inclusion - ≥ 18 years old; a primary clinical diagnosis in the ED (emergency department) of acute LRTI (< 28 days duration); clinician willing to consider procalcitonin in antibiotic decision-making. Exclusion – systemic antibiotics before ED presentation; current vasopressor use; mechanical ventilation (via endotracheal tube); known severe immunosuppression; accompanying non-respiratory infection; known lung abscess/empyema; chronic dialysis; metastatic cancer; surgery in the past 7 days (excluding minor surgery); incarcerated or homeless; enrolled in ProACT in the past 30 days.

Study type:	Patient-level, multi-center, randomized, combined superiority (primary outcome) and non-inferiority (primary safety outcome) trial
Date of first enrollment:	November 2014
Target sample size:	1674
Recruitment status:	Enrollment phase
Primary outcome(s):	Total antibiotic exposure, defined as the total number of antibiotic-days by Day 30

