- vii. subsequent hospitalization (for both those discharged from ED and those admitted to hospital)

v. SAMPLE SIZE

We desire at least 80% power to conduct our primary hypothesis tests using a one-sided significance level of 0.05. As shown below, determination of sample size was dependent on the hypothesis test for the primary safety outcome, as this required a larger sample size than the tests for antibiotic exposure. Analyses were performed with SAS 9.1 (SAS Institute, Inc., Cary, NC). **Allocation of 757 subjects in each arm (total trial sample size of 1514) meets our goal of at least 80% power.**

Testing H1: Procalcitonin guideline implementation reduces the total number of antibiotic-days by Day 30.

For H1, ProHOSP reduced antibiotic exposure from 8.7 to 5.7 days (35% relative risk reduction). We chose a 20% relative reduction as an appropriate minimum threshold and to detect a lower effect size than ProHOSP.

We assumed control arm antibiotic exposure of 8 days, and calculated sample size based on a two-sided two-sample test at 0.05 significance. Under these assumptions, the sample size of 1514 required for H2 provides >99% power to detect a 20% relative reduction, and 80% power to detect a reduction of as low as one antibiotic-day (12% relative reduction). Power is preserved under a wide range of assumptions. Thus, we are exceptionally well-powered for H1.

Testing H2: Procalcitonin guideline implementation does not increase the proportion of subjects who experience a composite endpoint of adverse outcomes by Day 30.

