**POWER AND SAMPLE SIZE**

The sample size was driven by the safety aim ( $H_2o$ ) due to the non-inferiority hypothesis and the binary nature of the outcome. The original sample size of 1,514 participants (757 per arm) was based on the differences in proportions in the composite adverse outcomes endpoint between the two arms. Our power calculations accounted for two interim analyses at approximately 1/3 and 2/3 enrollment with stopping boundaries calculated using the O'Brien and Fleming method,  $\geq 80\%$  power to reject  $H_2o$ , and a predefined 4.5% noninferiority margin. The noninferiority margin was chosen based on clinical meaningfulness and feasibility within funding constraints. It is approximately half that of the Infectious Diseases Society of America's recommendation and of two large trials of procalcitonin antibiotic guidance [10, 18].

We assumed 11% adverse outcomes by Day 30 in the usual care arm [19, 20] and a 10% loss to follow up for the original sample size estimate. We prospectively monitored both frequencies based on the overall blinded sample with intent to recalculate and adjust the sample size as necessary. The use of blinded data for the recalculation ensures that the overall significance level is 0.05. After approval by the DSMB in April 2017, the sample size was increased to 1,664 participants.

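### Protocol version 1.4 gives two trial sizes (1674 and 1514), the SAP gives a third (1,664), and the only stated power belongs to the smallest

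*Protocol*

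**What the plan says.** The protocol's cover page reads "FINAL PROTOCOL DATE: Version 1.4, March 8, 2017". The registration table of that version gives "Target sample size: 1674".

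Section 2.A.v (Sample size) of the same version rests its claim of at least 80% power on 757 per arm, a "total trial sample size of 1514". Under H2 it assumes an 11% composite event rate, a 4.5-point margin, no true difference and about 10% loss to follow-up. The section opens with a one-sided 0.05 level. It mentions neither 1674 nor 1,664.

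The SAP (Power and sample size) treats the protocol's number as history: "The original sample size of 1,514 participants (757 per arm) was based on the differences in proportions". It says that event rate and loss were monitored on blinded pooled data so that the size could be adjusted, and then: "After approval by the DSMB in April 2017, the sample size was increased to 1,664 participants". The SAP abstract reports 1,664 randomized. The SAP does not mention 1674. It gives no observed event rate, no observed loss and no power for 1,664.

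Protocol section 3.B requires a formal amendment when the sample size changes.

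**The concern.** 1674 and 1514 are both current text of one protocol version, so this is not a leftover in a change log. The SAP's account covers the step from 1514 to 1,664 but leaves 1674 unexplained, and 1674 was already in print a month before the approval that the SAP dates to April 2017.

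The safety conclusion is a non-inferiority claim, and both documents say that H2 drove the sample size. A reader should be able to find one size, its assumptions and its power. As it stands, the only written power belongs to a size the SAP calls original. The size was raised, which suggests that a monitored input had moved from plan. If so, power at 1,664 under the updated inputs cannot be recovered from the documents.

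**Working it through.** **Inputs.** Event rate 11% in both arms, margin 0.045, true difference 0, one-sided 0.05, 10% loss (protocol 2.A.v); 1:1 allocation (protocol 2.B.i); looks at about 1/3, 2/3 and the end of enrollment (SAP, Power and sample size); H2 boundaries: efficacy -3.26, -2.16, -1.71 and interim futility 0.55, -0.87 (SAP Table 2).

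**Step 1: fixed design.** n per arm = (1.645 + 0.842)² × 2 × 0.11 × 0.89 / 0.045² = 598, so 1196 in total, and 1196 / 0.9 = 1329 with 10% loss.

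At 1514, evaluable n per arm = 757 × 0.9 = 681.3. SE = √(0.1958 / 681.3) = 0.01695. Power = Φ(0.045 / 0.01695 - 1.645) = Φ(1.01) = 84.4%. The same formula gives 87.2% at 1664 (748.8 per arm) and 87.4% at 1674 (753.3 per arm).

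**Step 2: Table 2 boundaries.** The three-look design was evaluated with equally spaced information, first stopping whenever a futility bound is crossed (binding), then ignoring futility (non-binding).

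| Total size | Futility binding | Futility non-binding |
|---|---|---|
| 1514 | 80.8% | 83.4% |
| 1664 | 84.0% | 86.4% |
| 1674 | 84.2% | 86.5% |

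The claim of at least 80% at 1514 therefore reproduces. Simulation error is about 0.1 point. The SAP (Interim analyses) says that the DSMB could have recommended stopping, which suits the non-binding column better, but both are shown.

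**Step 3: the 1664 to 1674 gap.** This is 10 patients, or 10 / 1664 = 0.6%, and about 0.2 points of power. It is a documentation matter.

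**Step 4: which rule decides H2.** SAP Analysis of primary outcomes declares non-inferiority when the upper limit of a two-sided 95% interval is below 4.5%. That is a critical value of 1.96 at the final look, stricter than the 1.71 in Table 2. With the interim boundaries unchanged, 11% events and 10% loss:

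| Total size | Futility binding | Futility non-binding |
|---|---|---|
| 1514 | 75.7% | 77.2% |
| 1664 | 79.4% | 80.8% |
| 1674 | 79.6% | 81.1% |

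**Step 5: what 1,664 might reflect (illustration only).** Suppose 1,664 was chosen to restore the power of the 1514 design.

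- If only the event rate moved: p(1 - p) = 0.0979 × 1664 / 1514 = 0.1076, so p = 12.3%.
- If only the loss moved: 1 - 1514 × 0.9 / 1664 = 18.1%.

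Either change brings power at 1664 back to about 81% under Table 2 with binding futility. Neither rate is in the documents.

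**The case against.** The strongest reply is that the later document settles the matter. The SAP names the final size, the blinded mechanism and the approving body, and reports the same number randomized. Enrollment is complete, and non-inferiority will be judged by the observed confidence limit, not by planned power. Correcting a table changes no margin, estimate or decision rule. All of that stands, and it limits the point to consistency and reporting.

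Three stronger readings are tempting, and the documents do not support them.

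- *That the sample-size calculation is wrong.* It is not: 1514 reproduces its stated power from its own inputs, and under the same assumptions a larger trial can only have more.
- *That 1,664 leaves the trial underpowered.* The revised inputs are not given, so this cannot be shown. The 12.3% and 18.1% figures are back-solved assumptions. The 17% rate that the protocol quotes from ProHOSP is not a fair benchmark: protocol section 1.B says that trial's composite included ICU admission, which is not in this one.
- *That a larger figure in March 2017 and an approval in April 2017 point to an irregular or unblinded change.* The SAP dates the approval, not the calculation. A March figure is compatible with a proposal awaiting approval. The second interim analysis was also completed in April 2017, but the SAP says that the recalculation used blinded data and nothing contradicts it.

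What the reply does not answer is that 1674 has no explanation anywhere and that 1,664 has no stated inputs or power.

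**Conclusion.** The point holds as a contradiction in current text together with an under-documented re-estimation. Three sizes appear, one is unexplained, and the only power statement is tied to the size that was replaced.

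On the documents' own assumptions all three sizes meet the 80% goal under Table 2. They do not clearly meet it under the two-sided 95% interval: 1514 falls short by about 3 to 4 points, and 1664 and 1674 sit at roughly 80%.

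These figures assume equal event rates in the two arms, equally spaced looks, a normal approximation and the planned 10% loss. Power under the rates that prompted the increase remains unknown.

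**What to change.** 1. Put one reconciled size in the protocol's registration table, in protocol section 2.A.v and in the SAP. State what 1674 was and how it relates to 1,664.
2. Replace the power statement for 1514 with the power at the reconciled size. Report the blinded pooled event rate and loss that drove the re-estimation, and the date of that calculation as distinct from the date of DSMB approval.
3. State that power under the rule that will decide H2, naming either the two-sided 95% interval or the -1.71 final bound, and say whether futility was treated as binding.
4. If a range of event rates or losses is shown, label values such as 12.3% or 18% as illustrative, and do not use 17% as a benchmark.

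The cost is wording only. No patients, data or analyses are added. The stated power may become slightly less favorable.

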2 METHODS

A. PARTICIPANTS, INTERVENTIONS, AND OUTCOMES

i. STUDY SETTING

Screening and enrollment will occur in the EDs from approximately 14 sites across the US, with the University of Pittsburgh serving as the Coordinating Center. Sites were chosen based on the following considerations: sample size and projected recruitment rates; site willingness and ability to institute all required study interventions successfully and appropriately; and generalizability of findings.

ii. ELIGIBILITY CRITERIA

a. PARTICIPANT INCLUSION CRITERIA

1. ≥ 18 years old
2. A primary clinical diagnosis in the ED of acute LRTI (< 28 days duration)
3. Clinician willing to consider procalcitonin in antibiotic decision-making

LRTI will be classified after enrollment into the following categories:

- (i) Community acquired pneumonia (CAP)²¹
- (ii) COPD exacerbation
- (iii) acute asthma exacerbation
- (iv) acute bronchitis
- (v) other LRTI

b. PARTICIPATION EXCLUSION CRITERIA

Conditions where physicians are unlikely to withhold antibiotics

1. Systemic antibiotics before ED presentation
 - a. All prophylactic antibiotic regimens, OR
 - b. Received >1 dose within 72 hours prior to ED presentation
2. Current vasopressor use
3. Mechanical ventilation (via endotracheal tube)
4. Known severe immunosuppression
5. Accompanying non-respiratory infections
6. Known lung abscess or empyema

Conditions where PCT can be > 0.25 ug/L without infection

7. Chronic dialysis
8. Metastatic cancer
9. Surgery in the past 7 days (excluding minor surgery such as skin biopsy)

Conditions rendering follow-up difficult:

10. Incarcerated or homeless
11. Enrolled in ProACT in the past 30 days

iii. STUDY INTERVENTIONS AND PROCEDURES

After written informed consent is obtained, participants will be randomized and enrolled into one of two different study groups: the procalcitonin group or the usual care (UC) group.

Study procedures specific to the procalcitonin group:

In the procalcitonin group, the intervention consists of reporting procalcitonin results and the procalcitonin antibiotic guideline to clinicians, while embracing clinician autonomy. Study staff will be trained to inform clinicians that the procalcitonin information is available, and not to otherwise influence care. At all times, the clinician retains complete decision-making authority. **The final decision to give antibiotics is at the discretion of the treating clinician.**

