There may not be a direct benefit from taking part in this research study. For participants in the procalcitonin group, clinicians may use the procalcitonin levels to make more informed decisions about current treatment planning. It is possible that study findings will help future patients with lower respiratory tract infections.

B. ASSIGNMENT OF INTERVENTIONS

i. ALLOCATION

a. SEQUENCE GENERATION

Participants will be randomly assigned to control or intervention group with a 1:1 allocation as per a computer generated randomization schedule stratified by site, race, and age using permuted blocks of random sizes for each enrolling site. The block sizes will not be disclosed to ensure concealment.

b. ALLOCATION CONCEALMENT MECHANISM

Allocation concealment will be ensured, as the ProACT coordinating center data management team will not release the randomization group until the participant has been recruited into the trial, which takes place after all required pre-randomization data have been completed and entered into the study eDCF.

c. IMPLEMENTATION

All participants who give consent for participation, fulfill inclusion criteria, and do not meet exclusion criteria will be randomized. Randomization will be conducted without any influence of the principal investigator, site study team, or ProACT coordinating center study team. Following participant recruitment, the site study team member will enter participant information into the eDCF and receive from the randomization system a study ID # and treatment assignment. In the rare case of eDCF malfunction, manual randomization will occur. Random assignment will be determined by a coin-flip method performed by the ProACT medical monitor and treatment assignment and subject ID# will be communicated to the ProACT coordinating center data team and site study team. All pre-randomization data will then be sent to the ProACT coordinating center study team to be entered into the eDCF.

d. BLINDING

Due to the nature of the intervention, neither the treating clinician nor the study staff can be blinded to allocation in the ED. ProACT coordinating center research staff conducting post-discharge follow up will be blinded to allocation.

ii. DATA COLLECTION, MANAGEMENT, AND ANALYSIS

a. DATA COLLECTION METHODS

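### If antibiotic exposure is not reduced, the protocol's exception for low control-arm use allows a conclusion that the two-arm design cannot support

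*Protocol*

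**What the plan says.** Protocol section 2.B.ii.c (Statistical methods), under Potential outcomes of proposed approach, sets out how results other than the hoped-for one would be read. For a null result on antibiotic exposure (H1) it gives a default: "Taking this finding in isolation, we would not recommend procalcitonin guideline implementation". An exception follows, triggered "if this finding is due to lower control arm antibiotic use relative to common clinical practice". In that case "we would conclude hospitals could choose either procalcitonin guideline implementation or compliance with current guidelines to reduce antibiotic use".

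The only unfavourable safety scenario written out there is "Antibiotic exposure is reduced, but safety worsens". Failure to reduce exposure combined with failure to show non-inferiority on safety is not discussed.

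On the design, the registration table describes the control as "Usual care; no procalcitonin results will be reported to treating clinicians", and section 2.B.i.a states "Participants will be randomly assigned to control or intervention group with a 1:1 allocation". Section 2.A.iii leaves all care in the control group to the treating clinician. The SAP does not repeat the exception and offers no other reading of a null H1.

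**The concern.** The exception attaches a conclusion about two strategies to a negative primary result. One of those strategies, adherence to existing guidelines, is not studied. The other, procalcitonin guidance, will by assumption have failed to beat usual care.

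Whether the exception applies rests on a causal judgement, that the null arose because control use was low against outside practice. Nothing in either document says how to make that judgement, and it would be made once the results are known. At stake is what the trial may claim after a null H1. A reader could be told that procalcitonin is a reasonable way to cut antibiotic use when the randomised comparison did not show it, and without reference to the safety result.

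**Working it through.** The question is one of inference, so the first part sets the exception against the design. The arithmetic that follows is illustrative.

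**1. What the exception needs and what the design supplies**

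- *Evidence on guideline adherence.* There are two arms, procalcitonin and usual care. SAP Table 1 lists no measure of adherence to existing guidelines. The SAP's congruence measure (Accounting for Non-Compliance) concerns the procalcitonin guideline and is defined only in the intervention arm.
- *A benchmark for ordinary practice.* None is designated. Protocol 2.A.v has two possible figures: 8 days, assumed for the control arm, and 8.7 days, the control value in the earlier six-centre trial. Both serve planning. They differ by 8.7 - 8 = 0.7 day, so a control mean between them would be low against one and not the other. Data on patients who refuse consent (2.A.vi) cover participation, sex, age and race, not antibiotic use.
- *Evidence that procalcitonin reduces use.* H1 is a superiority test, and no equivalence margin for antibiotic-days is given.
- *A safety condition.* The exception does not mention H2.

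**2. Where a claimed reduction would come from**

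For mean antibiotic-days:

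procalcitonin - outside practice = (procalcitonin - usual care) + (usual care - outside practice)

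Randomisation protects only the first bracket. When H1 is not rejected, that bracket has not been shown to be below zero. Any reduction credited to procalcitonin then rests on the second bracket, an uncontrolled comparison with no designated data source.

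**3. What a null H1 would leave open**

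Inputs from Protocol 2.A.v: 757 per arm, two-sided 0.05, control mean 8 days, 80% power for 1 day and more than 99% for a 20% reduction (1.6 days). The SD is not stated, so it is solved from the 80% figure:

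- SD = 1 x sqrt(757/2) / (1.960 + 0.842) = 19.46 / 2.802 = 6.94 days
- Standard error of the difference = 6.94 x sqrt(2/757) = 0.357 day
- Power for 1.6 days = Phi(1.6/0.357 - 1.960) = Phi(2.52) = 99.4%

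This reproduces the plan's figure of more than 99%. It shows that the two stated powers agree with each other; it does not verify the SD.

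- 95% CI half-width = 1.960 x 0.357 = 0.70 day

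The half-width follows automatically from 80% power for one day (1.960/2.802 = 0.70), so it does not measure the defect. It only shows what a null result means. An estimate of -0.2 day, chosen for illustration, would have an interval of about -0.9 to +0.5 day, which includes an increase in use.

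**4. The scenario named by the trigger**

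Power for a true 20% reduction with SD held at 6.94 is Phi(0.2 x control mean / 0.357 - 1.960):

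- control mean 8 days: 99%
- 6 days: 92%
- 5 days: 80%
- 4 days: 61%
- 3 days: 39%

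If the SD instead shrinks in proportion to the mean, power stays at 99% throughout. With low control use, a null H1 may therefore be a missed true reduction or a real absence of effect, depending on an SD the documents do not give. Neither case shows that the two named strategies are interchangeable.

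**The case against.** The strongest reply is that this is discussion prose, not an analysis rule. It sits beside remarks on patent expiry and assay price, the SAP does not carry it, and the tests are governed by the SAP's Study Hypotheses and Analysis of Primary Outcomes. The wording is permissive and conditional, and it adds a premise about control use instead of arguing from non-significance alone. All of this is fair. It limits the consequence to interpretation, but the added premise still cannot be checked with what the plan provides.

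Four stronger readings are tempting, and the documents do not support them:

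- *That the protocol would favour procalcitonin whenever H1 fails, or contradicts itself.* The default is not to recommend it. The default is expressly limited to the finding taken alone, and a conditional exception follows.
- *That the design has no safety condition.* H2 is a primary non-inferiority test with a 4.5% margin. Protocol 2.B.ii.c defers it to the final analysis if H1 is not rejected at the second interim, and the DSMB could stop for harm. The SAP did allow an interim stop for H1 futility, but it reports both interim looks completed and 1,664 patients randomised. What is missing is a link between H2 and this conclusion.
- *That no practice figures exist.* Two planning values are given; neither is designated as the benchmark.
- *That the design lowered control-arm use.* Eligibility requires "Clinician willing to consider procalcitonin in antibiotic decision-making", and section 2.B.iii.c adds "We will also conduct basic in-servicing to raise clinician awareness of the study and the procalcitonin algorithm". With patient-level randomisation within sites, the same clinicians could treat controls. These features make low control use ambiguous, but nothing in the documents shows that they reduced it.

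**Conclusion.** The exception is wrong as written. Followed literally after a null H1, it yields a conclusion that the trial cannot support, for four reasons: one named strategy is untested, the trigger has no benchmark, non-rejection of superiority is not evidence of a reduction, and the H2 result is not required. The first, second and fourth rest on the text alone. The third needs only that no equivalence margin for antibiotic-days is set.

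The defect has no numerical size. The 0.70-day half-width and the power figures at lower control means are illustrations that assume a back-solved SD of 6.94 days. The exception applies only if H1 is not rejected, and it changes no test, boundary, endpoint or sample size.

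**What to change.** In Protocol 2.B.ii.c, delete the sentence that begins with the low-control-use condition. Replace it with wording such as: if H1 is not rejected, the conclusion is that a reduction in antibiotic exposure was not demonstrated; the difference and its confidence interval are reported together with the H2 result, whichever way H2 falls; and no recommendation in favour of implementation is made. The control-arm level of antibiotic use may be described, but only as hypothesis-generating context for generalisability. Repeating this in the SAP would put the reading of a null H1 beside the tests it refers to.

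A weaker alternative is to keep the sentence, name the benchmark and its source, require H2 non-inferiority and label the conclusion hypothesis-generating. That would still supply no evidence on adherence to existing guidelines, so deletion is cleaner.

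The cost is wording only, with no change to tests, sample size or data collection. The sponsor gives up a favourable fallback interpretation.
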